9.1. Statistical Hypotheses

The primary efficacy objective will be assessed using a Natural Cubic Spline (NCS) model with 2 degrees of freedom of the primary outcome iADRS at Month 18.

The primary efficacy analysis will be conducted on two populations: the intermediate tau population at baseline and the overall population. The hypothesis will be tested with a control of family wise 2-sided type I error rate of 5% following the chain procedure (Millen and Dmitrienko 2011).

The testing scheme, and a graphic testing procedure that will be used to control the overall false positive rate for the primary endpoint and major secondary endpoints will be described in the Study SAP.

Major secondary hypotheses defined in a similar manner are that donanemab is superior to placebo with regard to:

- Clinical progression in participants with early symptomatic AD through Week 76, as measured by MMSE, ADAS-Cog₁₃, CDR-SB, and ADCS-iADL
- Brain amyloid deposition at Week 76 measured by florbetapir F18 PET scan
- Brain tau deposition at Week 76 measured by flortaucipir F18 PET scan
- Brain region volumes at Week 76 measured by vMRI

9.2. Sample Size Determination

Approximately 1800 participants will be randomly assigned in the study. It is anticipated that approximately two-third of participants have low-medium tau and approximately one-third of participants have high tau pathology.

The powering and sample size determination of the trial is based on the low-medium tau pathology population. The assumptions for the power calculation were based on the results of the Study AACG data. The mean progression levels in the placebo and donanemab arms from the MMRM analysis on iADRS were -10.06 and -6.86 points (approximately 32% slowing) over 18 months, respectively, with a standard deviation of 11.06. The assumed discontinuation rate of AACI is 30%. Multiple longitudinal datasets were simulated, and the NCS model with 2 degrees of freedom was fit to each sample to determine the power. With a sample size of approximately 1000 randomized participants in the low-medium tau pathology population, the NCS model with 2 degrees of freedom provides greater than 95% power to achieve statistical significance at a 1-sided 0.025 level for the treatment difference relative to placebo, as measured by iADRS at Month 18. If both treatment arms are placebo-like with no efficacy, the type I error is 2.5%.

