Study AACI expands the patient population compared to the prior Phase 2 study by including participants with high tau pathology. The primary analysis will test the low-medium (intermediate) tau pathology population and the overall population (low-medium and high tau pathology).

Objectives and Endpoints

Objectives	Endpoints
Primary	
To assess the effect of donanemab versus placebo on clinical progression in participants with early symptomatic AD	iADRS change from baseline through Week 76 in at least one of 
 • the low-medium tau pathology population or • the overall population
Secondary	
To assess the effect of donanemab versus placebo on clinical progression in participants with early symptomatic AD	Change from baseline through Week 76 in at least one of 
 • the low-medium tau pathology population or • the overall population as measured by: 
 • CDR-SB • ADAS-Cog₁₃ score • ADCS-iADL score • MMSE score
To assess the effect of donanemab versus placebo on brain amyloid deposition	Change in brain amyloid plaque deposition from baseline through Week 76 as measured by florbetapir F18 PET scan
To assess the effect of donanemab versus placebo on brain tau deposition	Change in brain tau deposition from baseline through Week 76 as measured by flortaucipir F18 PET scan
To assess the effect of donanemab versus placebo on brain region volumes	Change in volumetric MRI measures from baseline through Week 76

Objectives	Endpoints
To evaluate safety and tolerability of donanemab	Standard safety assessments: 
 • Spontaneously reported AEs • Clinical laboratory tests • Vital sign and body weight measurements • 12-lead ECGs • Physical and neurological examinations MRI (ARIA and emergent radiological findings) Infusion related reactions C-SSRS
To assess peripheral PK and presence of anti-donanemab antibodies	Plasma PK of donanemab ADAs against donanemab including 
 • treatment-emergent ADAs • neutralizing antibodies

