For between-group comparability, participant randomization will be stratified by investigative site and tau pathology (low-medium versus high). Assignment to treatment groups will be determined by a computer-generated random sequence using an IWRS. Randomization into 1 stratum may be discontinued at the discretion of the sponsor.

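### Does the power statement in Section 9.2 use the wrong number of low-medium tau participants and the wrong alpha level?

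*Protocol*

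**What the plan says.** Protocol Section 9.2 gives the total, "Approximately 1800 participants will be randomly assigned in the study", and the expected mix: "It is anticipated that approximately two-third of participants have low-medium tau and approximately one-third of participants have high tau pathology". It bases the sizing on the low-medium tau population. The assumptions are mean iADRS changes of -10.06 on placebo and -6.86 on donanemab over 18 months, a standard deviation of 11.06 and 30% discontinuation. The power sentence reads "With a sample size of approximately 1000 randomized participants in the low-medium tau pathology population", the spline model with 2 degrees of freedom gives "greater than 95% power to achieve statistical significance at a 1-sided 0.025 level". The section closes: "If both treatment arms are placebo-like with no efficacy, the type I error is 2.5" percent.

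Section 9.1 names two primary populations, intermediate (low-medium) tau and overall, tested with "control of family wise 2-sided type I error rate of 5% following the chain procedure". The objectives tables in Sections 1.1 and 3 word the primary endpoint as "iADRS change from baseline through Week 76 in at least one of" the two populations. Sections 9.1 and 9.4.1 leave the testing scheme to the Study SAP. Section 6.3 adds: "Randomization into 1 stratum may be discontinued at the discretion of the sponsor".

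**The concern.** Two inputs of the protocol's only sample size justification seem not to match the design.

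The first is the number. Two-thirds of 1800 is 1200, yet power is stated for about 1000, which is 56% of 1800. No reason is given.

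The second is the level. If the overall population can succeed when the low-medium population does not, as the wording of the endpoint suggests, it must hold some alpha from the start. The low-medium test would then begin below 1-sided 0.025, and a power quoted at the full level would be too high for that starting test. The closing 2.5% could also be misread as covering a procedure that the simulation did not include.

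At stake is whether the trial has the power it claims for its main population.

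**Working it through.** **Inputs.** From Section 9.2: difference 10.06 - 6.86 = 3.20 points, SD 11.06, 30% discontinuation, 1800 randomized, two-thirds low-medium tau. From Section 6.3: 1:1 allocation. The share of alpha given to the low-medium test is not in the protocol, so a range is shown.

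**Sample sizes.** 1800 × 2/3 = 1200; 1000/1800 = 0.556. Completers per arm are 1000/2 × 0.70 = 350, or 1200/2 × 0.70 = 420.

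**Reproducing the stated power.** The protocol simulated longitudinal data, which cannot be rerun from the text. A two-sample normal approximation on completers serves as a check:

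z = 3.20 / (11.06 × √(2/n)), power = Φ(z - z_α)

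- n = 350: standard error 0.836, z = 3.827. At 1-sided 0.025, power = Φ(3.827 - 1.960) = 96.9%, which agrees with the claim.
- n = 420: standard error 0.763, z = 4.193, power = Φ(4.193 - 1.960) = 98.7%.

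**Smaller alpha shares (assumed).**

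| 1-sided level | Share of 0.025 | Power, 1000 randomized | Power, 1200 randomized | Randomized N for 95% |
|---|---|---|---|---|
| 0.025 | all | 96.9% | 98.7% | 889 |
| 0.0125 | half | 94.4% | 97.5% | 1032 |
| 0.005 | one-fifth | 89.5% | 94.7% | 1218 |

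The last column is 2n/0.70, with n = 2 × [(z_α + 1.645) × 11.06/3.20]² rounded up to 311, 361 and 426 per arm.

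**Break-even.** Power is 95% when z_α = z - 1.645.

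- At 1000: z_α = 2.183, level 0.0145, a share of 0.0145/0.025 = 58%.
- At 1200: z_α = 2.548, level 0.0054, a share of 22%.

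**Closer to the planned model.** The completer approximation discards the visits of those who leave early, while the spline model uses them. An information calculation for the 2-degree-of-freedom spline assumed knots at Weeks 0, 36 and 76, the scheduled efficacy visits, dropout spread evenly up to 30%, and SD of change 11.06. It tried two random-slope covariances and one compound-symmetry covariance. For alpha shares from one-fifth to all, power was at least 96.5% at 1000 and at least 98.7% at 1200.

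**The case for a change.** The case for acting has substance. A gap of 200 is more than rounding, and Section 9.2 does not say that 1000 is a floor. The amendment history in Section 10.9 records a rise in the total from 1500 to 1800, and two-thirds of 1500 is 1000. The number may therefore be a carry-over, though that is inference. On alpha, giving the low-medium test everything at the start would leave the overall population unable to win alone, and the endpoint's wording would then have little content. On the completer approximation the two inputs also interact: at half the alpha, power falls just short of 95% at 1000 (94.4%) but not at 1200.

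Two parts stand: the 1000 is unexplained, and Section 9.2 does not name the level it assumes within the chain procedure. The rest does not carry through. About 1200 is an expected mix and about 1000 is the number at which power is stated, so both can be true. Stating power below the expected number is conservative, and it is prudent when one stratum may be closed early. The full 1-sided 0.025 is the default level for pairwise tests in Section 9.4.1, and a chain procedure may pass alpha to the low-medium test after a rejection in the overall population. Whether it starts lower depends on weights that the protocol properly leaves to the SAP. The closing 2.5% reads naturally as the null rejection rate of the one test simulated. Read as a 1-sided family-wise rate, it also agrees with the 2-sided 5% in Section 9.1. Nothing in the protocol proposes testing both populations at full alpha without adjustment.

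**Conclusion.** No change follows. The stated power is right for its own inputs (96.9% on completers against a claim of more than 95%). The mismatch in number errs on the safe side: moving from 1000 to the expected 1200 raises power by about 1.8 points at the full level. Splitting alpha could undo the claim at the expected 1200 only if the low-medium test began with less than about 22% of the alpha, and then only on an approximation that ignores partial follow-up. The spline calculation stays above 95% at both numbers for every share examined.

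This rests on the protocol's own effect, SD and dropout assumptions, on assumed alpha shares from one-fifth to all, and on the assumed covariances of the spline check. A sentence calling 1000 a conservative minimum and naming the alpha level would help a reader. It would be an editorial courtesy, because it would change neither enrolment nor the analysis, and no underpowering is shown.

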9.3. Populations for Analyses

The following populations are defined:

Population	Description
Entered	All participants who sign the ICF.
Enrolled/Intent-to-Treat	All participants assigned to treatment, regardless of whether they take any doses of study treatment, or if they took the correct treatment. Participants will be analyzed according to the treatment group to which they were assigned.
Efficacy Evaluable	All participants with a complete baseline assessment and at least 1 complete post-baseline assessment.* Participants will be grouped according to randomized treatment assignment (donanemab or placebo), even if the participant does not take the assigned treatment, does not receive the correct treatment, or otherwise does not follow the protocol.
Safety	All participants randomly assigned to IP and who take at least 1 dose of IP.

Abbreviations: ICF = informed consent form; IP = investigational product.

* For each assessment, the efficacy evaluable population will be defined as all participants with a baseline measurement and at least 1 complete post-baseline measurement for that respective assessment.

9.4. Statistical Analyses

9.4.1. General Considerations

Statistical analysis of this study will be the responsibility of the Sponsor or its designee.

Unless otherwise noted, all pairwise tests of treatment effects will be conducted at a 2-sided alpha level of 0.05 (or equivalently, a 1-sided 0.025 alpha level); 2-sided CIs will be displayed with a 95% confidence level. All tests of interactions between treatment and other factors will be conducted at an alpha level of 0.05.

Details on the testing strategy for the primary and key secondary analyses will be specified in the Study SAP.

All efficacy analyses will follow the intent-to-treat (ITT) principle unless otherwise specified. An ITT analysis is an analysis of data by the groups to which subjects are assigned by random allocation, even if the subject does not take the assigned treatment, does not receive the correct treatment, or otherwise does not follow the protocol.

When change from baseline is assessed, subjects will be included in the analysis only if both a baseline and a postbaseline measure are available. Unless otherwise defined, a baseline measure is the last nonmissing observation collected prior to the first administration of study medications. Endpoint is the last nonmissing postbaseline measurement.

For MMRM models, observations collected at nonscheduled visits will not be included in the analyses.

A database lock for the double-blinded phase primary efficacy analysis is expected to occur after all randomized subjects have had a chance to complete the double-blind period of the study. Efficacy and safety analyses will be conducted based on data collected during the double-blind period. Additional database lock(s) may occur. Additional efficacy and safety analyses will be conducted based on data collected during the extension period. Data collected during the immunogenicity and safety follow-up period will be summarized and analyzed separately.

The study will include several separate SAPs: a main study SAP (referred to as Study SAP) which will detail the analyses for the objectives for double-blinded, placebo-controlled phase, and a long-term extension (LTE) SAP which will detail analyses for the objectives of LTE phase. The analyses for any addenda such as analyses for open-label safety cohort will be included in a separate addendum-specific SAP.

The main Study SAP will be finalized prior to unblinding of all participants in the placebo-controlled phase. This section is a summary of the planned statistical analyses of the most important endpoints including primary and key secondary endpoints and a more technical and detailed description of the statistical analyses will be described in the SAPs.

Any change to the data analysis methods described in the protocol will require an amendment only if it changes a principal feature of the protocol. Any other change to the data analysis methods described in the protocol, and the justification for making the change, will be described in the Study SAP and the clinical study report. Additional exploratory analyses of the data will be conducted as deemed appropriate.

9.4.1.1. Handling of Missing Items for Scales

If any of the individual items for ADAS-Cog₁₃ or ADCS-ADL are missing or unknown, every effort will be made to obtain the score for the missing item or items. For ADAS-Cog₁₃, if 4 or fewer of a total of 13 items are missing, the total score (maximum = 85) will be imputed as follows: the total from remaining items will be multiplied by a factor that includes the maximum score for the missing items. For example, if the first item, “Word-Recall Task,” which ranges from a score of 0 through 10 (maximum = 10), is missing, and the second item “Commands,” which ranges from a score of 0 to 5 (maximum = 5), is missing, then the multiplication factor = $85/(85 - [10 + 5]) = 85/70 = 1.21$. Thus, the total score for this example will be the sum of the remaining 11 items multiplied by 1.21. The imputed number will be rounded up to the nearest integer. If more than 4 items are missing, the total score for ADAS-Cog₁₃ at that visit will be considered missing.

For the ADCS-iADL, if <30% of the items are missing, the total score will be imputed. The sum of the nonmissing items will be prorated to the sum of total items. The imputed number will be rounded up to the nearest integer. If the nearest integer is greater than the maximum possible score, the imputed score will be equal to the maximum score. If >30% of the items are missing, the total score for ADCS-iADL at that visit will be considered missing. The same imputation technique will be applied to the ADCS-ADL total score. Note that, depending on the specific item responses that are missing, it is possible to have an imputed total score for both the

DCS-iADL and the ADCS-ADL, an imputed total score for 1 but not the other, or both total scores missing.

The same imputation technique will be applied to the CDR-SB. If only 1 box (of 6) of the CDR is missing, the sum of the boxes will be imputed by prorating the sum from the other 5 boxes. If the score from more than 1 box is not available, the CDR-SB at that visit will be considered missing.

The iADRS score is calculated as:

$$\text{ADCS-iADL score} - \text{ADAS-Cog}_{13} \text{ score} + 85.$$

If either ADAS-Cog₁₃ or ADCS-iADL is missing, iADRS score will be considered missing.

For all other scales, if any item is missing, any total or sum involving that item will be considered missing.

9.4.2. Treatment Group Comparability

9.4.2.1. Participant Disposition

All participants who discontinue from the study will be identified, and the extent of their participation in the study will be reported. If known, a reason for their discontinuation will be given.

The reasons for discontinuation will be collected when the participant's participation in the study ends and will be summarized by treatment group for all randomized subjects. The percentage of subjects discontinuing from each treatment group will be compared between groups using Fisher's exact test. The comparisons will be done for the overall percentage of participants who discontinue and for select specific reasons for discontinuation.

9.4.2.2. Participant Characteristics

The participant's age, sex, race, height, body weight, body mass index (weight (kg) / [height (m)]²), tobacco use, alcohol use, caffeine use, years of education, work status, time since onset of first AD symptoms, time since diagnosis, baseline MMSE, ApoE genotype (E4 carrier versus non-carrier), having 1 or more first degree relatives with AD, and acetylcholinesterase inhibitor (AChEI) and/or memantine use at baseline will be recorded.

Baseline characteristics will be summarized by treatment group and overall. Summaries will include descriptive statistics for continuous and categorical measures. Fisher's exact test or Pearson's chi-square test will be used for treatment-group comparisons of categorical data. For continuous data, analysis of variance (ANOVA), with independent factors for treatment and investigator, will be used.

9.4.2.3. Prior and Concomitant Therapy

Prior medications are defined as those that stop before randomization (Visit 2). Concomitant medications are defined as those being taken on or after randomization (Visit 2). A summary of concomitant medications will be presented as frequencies and percentages for each treatment group. Fisher's exact test will be used to test for treatment differences between groups.

If the start or stop dates of therapies are missing or partial to the degree that determination cannot be made of whether the therapy is prior or concomitant, the therapy will be deemed concomitant.

Prior and concomitant medications will be listed.

Summary tables will also be provided for concomitant anticholinergics that affect cognitive function and AChEI/memantine medications.

Medications will be coded using the World Health Organization drug dictionary.

9.4.2.4. Treatment Compliance

Summary statistics for treatment compliance will be provided for the total number of complete infusions received, duration of complete infusion, and volume of complete infusion by treatment group.

Frequencies and percentages of reasons why infusion was stopped will also be presented.

9.4.3. Primary Endpoint(s)

The primary objective of this study is to test the hypothesis that IV infusion of donanemab will slow the cognitive and/or functional decline of AD as measured by iADRS score compared with placebo in the population of participants with intermediate tau pathology at baseline and the overall population.

A NCS analysis (Chambers and Hastie 1992) with 2 degrees of freedom (DF) will be used to assess the difference between treatment groups in iADRS score at Week 76. The NCS model provides a type of smoothing function to the data and can adequately estimate longitudinal trajectories under a variety of shapes (for example, linear and quadratic) for each treatment group. The degrees of freedom of the model can be prespecified to establish the level of smoothing of the data. The number and location of the “knots” is utilized to parse out different time periods where the data may transition from one shape to another to provide an adequate fit and the location of the knots will be provided in the SAP.

The iADRS score at baseline and at each of the postbaseline visits will be included in model as a dependent variable. Study visit will be treated as a continuous variable with values equal to weeks between baseline and postbaseline exam dates. The model will include these fixed effects: NCS basis expansion terms (2 terms), NCS basis expansion term-by-treatment interaction (2 terms), baseline age, concomitant AChEI and/or memantine use at baseline (yes/no), and potentially other covariates will be included in the model and specified in the Study SAP. An unstructured variance-covariance structure matrix will be used to adjust for intra-subject correlation. If the unstructured variance-covariance structure matrix results in a lack of convergence, the following structures will be used in sequence:

- Heterogeneous Toeplitz covariance structure
- Heterogeneous autoregressive order 1 covariance structure
- Heterogeneous compound symmetry covariance structure, and
- Compound symmetry covariance structure.

The primary time point for treatment comparison will be at Week 76.

The primary efficacy analysis may be modified to use an alternative statistical model based on interactions with regulatory agencies and/or internal decision making, and if modified, the model will be outlined in the Study SAP prior to unblinding of the placebo-controlled phase.

As a sensitivity analysis, a Bayesian Disease Progression Model (DPM) on the iADRS will evaluate possible slowing of disease progression with treatment of donanemab relative to placebo. The primary purpose of the DPM is to estimate a quantity known as the disease progression ratio (DPR), which measures the proportion of disease progression in donanemab-treated participants relative to placebo-treated participants.

The MMRM analysis will also be assessed for the iADRS. The change from baseline score on the iADRS at each scheduled postbaseline visit (according to the SoA) during the treatment period will be the dependent variable. The model for the fixed effects will include the following terms: baseline score, pooled investigator, treatment, visit, treatment-by-visit interaction, baseline-by-visit interaction, concomitant AChEI and/or memantine use at baseline (yes/no), and age at baseline. Visit will be considered a categorical variable. The null hypothesis is that the contrast between the donanemab group versus placebo at the last visit equals 0. An unstructured covariance matrix will be used to model the within-subject variance-covariance errors. If the unstructured covariance structure matrix results in a lack of convergence, the following tests will be used in sequence:

- heterogeneous Toeplitz covariance structure
- heterogeneous autoregressive covariance structure
- heterogeneous compound symmetry covariance structure
- compound symmetry covariance structure

The Kenward-Roger approximation will be used to estimate the denominator degrees of freedom.

The primary time point for treatment comparison will be at Week 76. The treatment group contrast in least-squares mean progression and its associated p-value and 95% CI will be calculated for the treatment comparison of donanemab versus placebo using the MMRM model specified above.

All analyses as described above, including the NCS with 2 DF, DPM, and MMRM models on iADRS will be assessed in the intermediate tau population and overall population.

Details about these analyses, as well as other sensitivity analyses including NCS with 3 degree of freedom, and quadratic models will be described in the SAP.

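### The fallback for the primary spline model ends in two compound-symmetry structures with no robust standard error; if either were reached with model-based errors, the Week 76 test could be too liberal (low severity)

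*Protocol*

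**What the plan says.** Section 9.4.3 makes iADRS at baseline and at every postbaseline visit the response of the primary spline model. The listed fixed effects are two spline terms, two spline-by-treatment terms and covariates. An unstructured covariance is planned. The rule for failure is: "If the unstructured variance-covariance structure matrix results in a lack of convergence, the following structures will be used in sequence". The order is heterogeneous Toeplitz, heterogeneous AR(1), heterogeneous compound symmetry, compound symmetry.

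The same order is given for the MMRM: "If the unstructured covariance structure matrix results in a lack of convergence, the following tests will be used in sequence". For that model only, the section adds: "The Kenward-Roger approximation will be used to estimate the denominator degrees of freedom". No standard-error method is named for the spline model, and no robust estimator is named for either model. Further detail is left to the SAP, which is not at hand.

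Section 9.1 promises "control of family wise 2-sided type I error rate of 5% following the chain procedure".

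**The concern.** A fallback covariance is harmless to the p-value only if the standard error remains valid when the structure is wrong. With baseline in the response and no treatment main effect listed, the Week 76 contrast is in essence a between-arm difference in within-person change. Its model-based standard error therefore depends on what the working covariance implies for the pair baseline and Week 76.

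Compound symmetry gives every pair of visits the same variance of difference, 2σ²(1 − ρ). The heterogeneous form lets this differ by pair, s₁² + s₂² − 2ρs₁s₂, but still imposes one correlation on visits 12 weeks apart and visits 76 weeks apart. If trajectories diverge over time, both tend to understate the variance of the long-range change.

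At stake is the validity of the pivotal p-value and confidence interval in the one situation the rule is written for. Choosing a different standard error after unblinding would look post hoc.

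**Working it through.** **Inputs from the protocol.** Section 9.2 gives mean changes on "iADRS were -10.06 and -6.86 points (approximately 32% slowing) over 18 months", "with a standard deviation of 11.06" (taken here as the SD of the 18-month change), 30% discontinuation and about 1000 low-medium tau participants. Allocation is 1:1. The Schedule of Activities places the scales at Weeks 0, 12, 24, 36, 52, 64 and 76, which is 7 time points.

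**Assumed, because the protocol does not give them.** Baseline SD 12-14, residual SD 4-6, intercept-slope correlation 0-0.2, a random intercept and slope, an interior knot at Week 36, and monotone dropout that is ignorable and spread evenly over visits.

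**1. The plan's own power.** The claim is more than 95% power "to achieve statistical significance at a 1-sided 0.025 level for the treatment difference relative to placebo". The difference is 10.06 − 6.86 = 3.20.
- With 1000 × 0.7 / 2 = 350 per arm, SE = 11.06 × √(2/350) = 0.836. Power = Φ(3.20/0.836 − 1.96) = Φ(1.87) = 96.9%.
- With 500 per arm, SE = 0.699 and power is 99.6%.

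The stated figure reproduces.

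**2. Why one common value fails.** Under a random slope, Var(change at week t) = 2r² + (11.06² − 2r²)(t/76)², where r is the residual SD. With r = 4:
- Week 76: 11.06² = 122.3.
- Week 12: 32 + 90.3 × (12/76)² = 34.3.

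Compound symmetry must give both the same value. Growth vanishes at r = 11.06/√2 = 7.82, where compound symmetry becomes exact.

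**3. Type I error.** Each working structure is set to its large-sample maximum-likelihood limit under the assumed truth. SE_model is what the software would report and SE_true is the sandwich value. Two-sided error = 2 × [1 − Φ(1.96 × SE_model/SE_true)].

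For compound symmetry, SE_model is 0.41-0.51 and SE_true is 0.69-0.76. At the ends of these ranges:
- 1.96 × 0.41/0.76 = 1.057, giving 29%.
- 1.96 × 0.51/0.69 = 1.449, giving 15%.

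Under the same assumptions, heterogeneous compound symmetry gives 12-24%, heterogeneous AR(1) about 2-3%, heterogeneous Toeplitz about 6%, and unstructured 5.0%.

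**4. Sensitivity to the assumed truth** (baseline SD 13, N = 1000, 30% dropout). Cells show SE_model/SE_true and the error.

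| True covariance | Toeplitz (het.) | AR(1) (het.) | CS (het.) | CS |
|---|---|---|---|---|
| Brownian, residual SD 4 | 0.738/0.760, 5.7% | 0.953/0.834, 2.5% | 0.516/0.788, 19.9% | 0.470/0.774, 23.4% |
| Random slope, residual SD 7 | 0.638/0.645, 5.3% | 0.979/0.885, 3.0% | 0.578/0.647, 8.0% | 0.557/0.646, 9.1% |
| Exact compound symmetry | 0.597/0.597, 5.0% | 0.942/0.863, 3.2% | 0.597/0.597, 5.0% | 0.597/0.597, 5.0% |

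Over a wider random-slope grid (baseline SD 10-16, residual SD 3-6), compound symmetry gives 15-35%, its heterogeneous form 11-31%, Toeplitz 5.3-7.4% and AR(1) 1.3-6.4%. With the sandwich standard error, the error is about 5% under every structure.

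**5. The MMRM.** Baseline is a covariate there, so less depends on the baseline-to-Week-76 correlation. Under the assumptions of step 3, compound symmetry gives about 10-16%, heterogeneous compound symmetry 5.5-6.0% and heterogeneous AR(1) 5.7-7.2%.

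**The case against.** The strongest reply is that this will not happen. The unstructured matrix has 7 × 8/2 = 28 parameters, against about 1000 participants in the smaller primary population and about 1800 overall. Heterogeneous compound symmetry is reached only after three successive failures, and compound symmetry only after four. This stands and sets the severity: the effect on the trial's actual error rate is that small probability times the conditional inflation.

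Second, the protocol nowhere says that the spline model's standard errors are model-based, and the SAP may specify robust ones. This also stands, so the point is conditional. For the MMRM, Kenward-Roger is an adjustment to the model-based covariance, so model-based inference is the natural reading there. For the spline model it is an inference from silence. The sequence of structures, however, is fixed in the protocol and can be judged there.

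Third, the size rests on a covariance that the documents do not give. This is correct, and the range for compound symmetry must be read as 5% to about 35%, depending on how fast variance grows.

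A reader might infer that any failure of the unstructured matrix pushes type I error well above 5%. The documents do not support that. The next step is heterogeneous Toeplitz, which stays near nominal, followed by heterogeneous AR(1), which in the spline model mostly costs power. Nor do the spline figures carry over to the MMRM, where the effect is smaller.

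**Conclusion.** The point holds in a narrow form and at low severity. The protocol prespecifies two last-resort structures for the primary model that, with model-based standard errors, would give a liberal Week 76 test if within-person variance grows with time. Under the stated assumptions the two-sided error is about 15-29% for compound symmetry and 12-24% for heterogeneous compound symmetry, against a nominal 5%. It falls to about 8-10% at residual SD 7 and to 5% when compound symmetry is true.

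The calculation is asymptotic, treats dropout as ignorable and assumes the knot position. The planned unstructured analysis keeps its 5% level, and neither the power figure nor the one-sided 2.5% in Section 9.2 is put in doubt.

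**What to change.** Add to Section 9.4.3, for both the spline model and the MMRM: *If any covariance structure other than unstructured is used, standard errors, tests and confidence intervals will use the empirical (sandwich) covariance estimator.*

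The cost is one sentence and one software option. The MMRM fallback would lose its Kenward-Roger degrees of freedom, which is immaterial at this sample size. The sandwich corrects the standard error only. It does not remove any bias in the estimate that a wrong covariance could cause when dropout depends on earlier scores, so unstructured should remain the planned choice.

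Deleting the two compound-symmetry steps instead is not advised. In the MMRM this would remove a structure that is close to nominal (5.5-6.0%) and keep heterogeneous AR(1), which is slightly worse (5.7-7.2%).
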